6.3 SUBJECT ENTRY

Patients who require cataract extraction and intraocular lens implantation will be screened for eligibility. If it is determined that the patient may be eligible to participate, study staff will explain the study purpose, procedures, risk/benefits and subject responsibilities to the potential participant. Written informed consent will be obtained prior to any study specific testing. The patient is enrolled upon signing the informed consent. The subject will sign and date the informed consent form in the presence of the person conducting the consent process. The investigator and/or the person conducting the consent process will also sign and date the consent form. The preoperative examination will be performed no more than 60 days prior to surgery. If the 60-day time period elapses, it is acceptable for patients to be re-screened by undergoing a complete preoperative examination.

Only subjects meeting all inclusion/exclusion criteria will be implanted. Those subjects who do not meet the inclusion/exclusion requirements will be considered screen failures. Subjects will continue to be enrolled until 500 subjects have been randomized and undergone implantation with the RxSight LAL or a monofocal IOL. If surgical complications occur and no LAL is implanted, the subject is exited from the study. Unique identification numbers will be assigned to each subject. The randomization schedules for each site will be prepared in advance and only the study statistician will have access to the randomization schedule. Prior to the surgical procedure, study site personnel will enter the subject's study ID into the study's EDC system and the treatment assignment (RxSight LAL or Control IOL) will be generated. Documentation of the randomization assignment for each subject will be maintained in the subject's file and in the EDC system.

The implant lens power for the RxSight LAL and the Control IOL will be calculated based upon the ocular biometry data and a standard IOL power calculation formula with the IOL closest to the post-surgical refractive target selected in an unbiased manner.

6.4 LAL IMPLANTATION AND REFRACTIVE ADJUSTMENT

6.4.1 SURGICAL PROCEDURE

The LAL will be implanted using standard microsurgical techniques.

No additional corneal refractive procedures are allowed until after the subject has been exited from the study.

The surgical procedure should be performed as follows:

- 1. Prepare and drape the eye for surgery in accordance with standard surgical procedures.
- 2. A clear corneal incision will be made using the surgeon's standard instrumentation and techniques.
- 3. Use viscoelastic to fill the anterior chamber through the incision opening.
- 4. Perform an anterior circular capsulorhexis standard technique. The capsulorhexis should be well-centered with a 360° overlapping capsular edge to minimize IOL tilt and decentration and longitudinal IOL shift. The capsulorhexis and/or nuclear fragmentation can be performed with a femtosecond laser. Precision pulse capsulotomy (PPC) can also be used to perform the capsulorhexis.
- 5. The surgeon will extract the cataract by phacoemulsification.
- 6. In the event of an intraoperative complication prior to implantation of the RxSight LAL, including posterior capsule rupture, zonular rupture, radial capsulorhexis tear, vitreous loss, iris trauma, corneal complications or any intraoperative abnormality that may affect the postoperative pupillary dilation, or the centration or tilt of the intraocular lens, do not implant the RxSight LAL.

- 7. The RxSight LAL will be introduced into the eye using the RxSight Insertion Device through a clear temporal corneal incision
- 8. Verify proper orientation of the RxSight LAL.
- 9. Aspirate any residual viscoelastic from the eye using a preferred technique.
- 10. The wound may close without suturing. If the unsutured wound is not watertight, close it with either a suture using standard technique or an ocular sealant (ReSure Sealant).
- 11. After completion of the surgery, ocular anti-inflammatory and/or antibiotic drops may be applied in accordance with standard clinical practice.
- 12. The subject will be provided with RxSight approved UV protective spectacles to protect the implanted RxLAL from extraneous sources of UV light. It is important to direct the subject to follow all instructions that are provided with the UV protective spectacles.

If a patch was used at the conclusion of surgery, the subject will wait for the surgeon to remove the patch. Once removed, the subject will begin wear of the UV protective eyewear as instructed.

6.4.2 LIGHT TREATMENT PROCEDURE

Seventeen (17) to 24 days after surgery, the subject will return for the Postop Week 3 evaluation and a 1st adjustment treatment of the RxSight LAL. Subsequent second and third adjustment treatments, if necessary, will all be separated by 3-7 days. The subject will receive the 1st lock-in treatment 3-7 days after the final adjustment treatment. If necessary, lock-in #2 may be performed 3-7 days after lock-in #1. Depending on the adjustment(s) performed, subjects will receive one to three adjustments and one or two lock-in treatments.

6.4.2.1 Postponement of Light Treatment Procedure(s)

LDD treatment should be delayed if any of the following new symptoms or changes in performance are noted;

- Color Vision Testing: Treatment should be delayed if the subject scores worse on Part 2 of the City University Color Test than the Pre-adjustment test for Tritan evaluation.
- Erythropsia Evaluation: With any score of 2 (red), the treatment should be delayed.
- Best Corrected Distance Visual Acuity: With any loss of BCDVA (unless the cause is known to be non-retinal) of 10 letters or more on an ETDRS (logMAR) chart compared to the Postop Week 3 BCDVA, treatment should be delayed.

- 6.4.2.2 Requirements for Additional Testing

Additional testing should be performed as soon as possible to evaluate whether UV-related retinal damage has occurred if any of the following is observed. will be performed in eyes that meet any of the following criteria:

- Significant erythropsia during in office erythropsia assessment (score of 2 (red))
- Significant erythropsia as indicated on responses to the Daily Life Erythropsia Ouestionnaire including:
 - o "severe" or "very severe" erythropsia on question 3, OR
 - o a response of "very bothersome" erythropsia on question 6, OR
 - o a response of "more than 7 days" on question 2
- Significant crythropsia as interpreted by the investigator based on spontaneous reports by the subject
- If the subject reports any level of erythropsia at the Postop Month 1-2 visit OR at any interim visit after the Postop Month 1-2 visit and <90 days after surgery based on results of the in office erythropsia assessment, the Daily Life Erythropsia Questionnaire or spontaneous verbal reports by the subject, the subject will be mailed a paper version of the Daily Life Erythropsia Questionnaire to self administer and return to the investigational site between 90-120 days after surgery. If responses to the Daily Life

² Azar D, Stark W, Dodick J, et al. Prospective, randomized vector analysis of astigmatism after three-, one-, and no-suture phacoemulsification. J Cataract Refract Surg 1997; 23:1164-1173.

Erythropsia Questionnaire indicate that there is erythropsia on question 1, the subject should have an unscheduled visit and testing should be performed.

- Any level of erythropsia at any unscheduled visit at 3-months or later or at the Postop Month 6 based on results of the in office erythropsia assessment, the Daily Life Erythropsia Questionnaire or spontaneous verbal reports by the subject
- Has a tritan anomaly (tritan score >1 on Part II of the 3rd Edition City University Color Vision Test (CUT) when tritan score was 0 pre-treatment) or an increase in tritan score of >1 at any time after light treatment
- Has an unexplained loss of best corrected distance visual acuity ≥2 lines compared to prelight-treatment at any visit (scheduled or unscheduled) after the first light treatment

[figure not shown]

testing should be repeated at subsequent study visit(s) following the diagnosis of retinal phototoxicity to assess subsequent changes. If a study eye is diagnosed with UV retinal damage, an additional follow-up exam will be added at 12 months postoperatively. Diagnostic imaging/testing of the fellow eye may be performed if in the opinion of the investigator additional information will aid in evaluation or diagnosis.

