6.6 EXAMINATION SCHEDULE

Subjects who agree to participate in the study will return for the listed follow-up examinations for each study eye:

Evaluation	RxSight LAL	- Control
Preoperative	Day -60 to Day -1	Day -60 to Day -1
Operative	Day 0, day of surgery	Day 0, day of surgery
Postop Day 1	Days 1 to 2 postop	Days 1 to 2 postop
Postop Week 1	Days 7 to 14 postop	Days 7 to 14 postop
Postop Week 3	Days 17 to 24 postop: Adjustment #1	Days 17 to 24 postop
Adjustment #2, if needed	3 to 7 days post Adjustment #1	
Adjustment #3, if needed	3 to 7 days post Adjustment #2	
Lock-in #1	3 to 7 days post final adjustment	
Lock-in #2, if needed	3 to 7 days post lock- in #1	
Postop Months 1-2	7 to 14 days post final lock-in visit	Days 30 to 60 postop
Postop Month 6	Days 120 to 180 postop	Days 120 to 180 postop
Postop Month 12, if needed	Days 330 to 420 postop	And the state of t

A Postop Month 12 visit will be conducted if a subject is diagnosed with UV retinal damage to confirm resolution or document sequelae, if any.

Unscheduled visits falling outside the designated ranges for scheduled visits will be considered "interim" visits for data recording purposes and a report form will be completed.

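### In the visible text, a DLEQ response that triggers testing for UV retinal damage does not also delay the next LDD treatment; confirm against the unredacted protocol

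*Combined protocol and SAP*

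**What the plan says.** **Delay rule (Section 6.4.2.1).** "LDD treatment should be delayed if any of the following new symptoms or changes in performance are noted". Three items follow:

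- Colour vision: "Treatment should be delayed if the subject scores worse on Part 2 of the City University Color Test", compared with the pre-adjustment test.
- Erythropsia: any score of 2 (red).
- BCDVA: a loss of at least 10 ETDRS letters from Postop Week 3, unless the cause is known to be non-retinal.

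**Testing rule (Section 6.4.2.2).** "Additional testing should be performed as soon as possible to evaluate whether UV-related retinal damage has occurred if any of the following is observed". The list that follows includes an in-office score of 2. It also includes "Significant erythropsia as indicated on responses to the Daily Life Erythropsia" Questionnaire, with three qualifying answers: severe or very severe on question 3, very bothersome on question 6, or more than 7 days on question 2. Further entries are significant erythropsia "as interpreted by the investigator based on spontaneous reports by the subject", a tritan criterion that includes "an increase in tritan score of >1 at any time after light treatment", an unexplained BCDVA loss of at least 2 lines, and two entries for erythropsia at later visits.

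**After a diagnosis.** Section 6.4.2.2 says that "testing should be repeated at subsequent study visit(s) following the diagnosis of retinal phototoxicity to assess subsequent changes", and Section 6.6 says that "A Postop Month 12 visit will be conducted if a subject is diagnosed with UV retinal damage". The Synopsis and Sections 4 and 6.9.1 repeat the Month 12 examination. None of these places mentions light treatments still to be given.

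**Timing.** Table 1 schedules the DLEQ at Postop Week 3 and at every adjustment and lock-in visit. Section 6.4.2.3 asks for the required measurements before each treatment.

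**The concern.** The protocol treats certain DLEQ answers as serious enough to look for UV retinal damage, which is one of the study's two safety questions (Section 3). The treatment under suspicion is repeated every 3 to 7 days. One would therefore expect a trigger for damage testing also to pause the next dose until someone has looked at the result. The visible delay list does that for the in-office red score, for any tritan worsening and for the BCDVA loss, but not for the DLEQ or for spontaneous reports.

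The in-office rule does not stand in for the DLEQ. Section 7.6.3 defines the 0/1/2 scale (white, pink, red) as the in-office assessment and summarises the DLEQ separately; Table 1 also gives them separate rows. A subject could report severe erythropsia in daily life and still score 0 or 1 in the office. On the visible wording, that eye is sent for testing but could receive its next UV dose before the result is reviewed.

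**Working it through.** The plan states no figure to reproduce. The check matches the two lists and works out when the triggers can occur.

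**1. Which testing triggers can arise while light treatments remain?** Inputs: first adjustment on Days 17 to 24; later treatments 3 to 7 days apart; at most three adjustments and two lock-ins (Section 6.4.2).

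- Latest scheduled light treatment: Day 24 + 4 × 7 = Day 52.
- The Months 1-2 visit follows the final lock-in by 7 to 14 days, so at the latest it falls on Day 52 + 14 = Day 66.
- Section 6.4.2.2 has seven triggers. Two (the route starting at Months 1-2, and erythropsia at 3 months or later) normally fall after the last lock-in. Five remain.

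**2. Matching the five to Section 6.4.2.1.**

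| Testing trigger | Visible delay item | Covered? |
|---|---|---|
| In-office score of 2 | Same score | Yes |
| Tritan increase of more than 1 from pre-treatment | Any worsening from pre-adjustment (wider) | Yes |
| Unexplained BCDVA loss of at least 2 lines | Loss of at least 10 letters; 10 / 5 letters per ETDRS line = 2 lines | Yes |
| DLEQ question 3, 6 or 2 | None | No |
| Spontaneous erythropsia judged significant by the investigator | None | No |

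Three of five are covered and two are not. This counts criteria; it does not measure risk.

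**3. At how many visits can the gap arise?** Days after Adjustment #1 on the longest course:

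- Adjustment #2: 3 to 7
- Adjustment #3: 6 to 14
- Lock-in #1: 9 to 21
- Lock-in #2: 12 to 28

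The shortest course has only Lock-in #1, at 3 to 7 days. So DLEQ questions 3 and 6, and spontaneous reports, can arise at 1 to 4 treatment visits after first UV exposure.

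The wording of question 2 is not shown. If it asks about duration since light treatment (an assumption), an answer of more than 7 days is impossible at the first of these visits, where the maximum is 7. It is then reachable at 0 of 1 visit on the shortest course and at up to 3 of 4 on the longest. Without that assumption the figures are 1 of 1 and 4 of 4.

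**4. Does other visible text supply a hold?**

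- Section 6.4.2.3 puts measurements before treatment but does not make treatment depend on them.
- Section 6.4.2.2 asks for testing as soon as possible, which sets no order relative to the next dose.
- The adjustment and lock-in steps in Sections 6.4.2.4 and 6.4.2.5 contain no such condition.
- The visible consequences of a diagnosis are repeat testing and the Month 12 examination only.

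**The case against.** **Removed text.** The strongest objection is that a hold may sit in text we cannot see. The delay list ends in a stray bullet, the lead-in to Section 6.4.2.2 is broken, and a gap follows its trigger list just before the sentence on phototoxicity. Assessment items and Table 1 row labels are also missing. A reader might infer that the protocol has no hold on these triggers. The documents do not support that, because redacted text is not absent from the plan. This objection stands and makes the point conditional.

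**Testing probably comes first.** The DLEQ is second in the assessment order (Section 6.7), a Table 1 footnote makes certain tests required once a Section 6.4.2.2 event occurs, and Section 6.4.2.3 puts required measurements before light. Together these plausibly place the additional tests before treatment at that visit. That narrows the gap, but no visible sentence says that treatment waits for the result to be reviewed.

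**Investigator judgement and general duties.** Section 8 puts subject welfare first when adverse events occur, and Section 8.2 asks for treatment that protects it. A reader might infer that investigators would treat an eye under work-up for phototoxicity, or that eyes will be harmed; nothing in the documents shows either. Still, a general duty is not a hold. The argument carries most weight for spontaneous reports, where the trigger is already the investigator's own judgement.

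**Different purposes.** The study asks about damage that routine testing may miss, which favours a wide testing net, and a DLEQ-positive eye still faces the three existing holds. That is a fair reason for the lists to differ. It does not explain why an eye thought to need damage testing should not wait for that result.

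**Conclusion.** The point holds in conditional form. In the visible text, a significant DLEQ response triggers testing for UV retinal damage but is not a reason to delay the next LDD treatment, and nothing visible makes treatment wait for the result. The same applies, with less force, to spontaneous erythropsia that the investigator judges significant. If the unredacted Sections 6.4.2.1 and 6.4.2.2 already contain a hold, the point falls away.

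The documents do not give the share of LAL eyes that would meet only a DLEQ or spontaneous-report criterion, so the number affected is unknown. Reading two uncovered criteria of five as a proportion of risk would be wrong. Sample size, power and alpha are not involved.

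Severity is low to moderate: a stated safety rule is narrower than the protocol's own triggers for suspected damage, and aligning them takes one sentence. Confidence is medium because of the removed text.

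**What to change.** First, the sponsor checks the unredacted Sections 6.4.2.1 and 6.4.2.2 for a hold on these two triggers. If there is one, nothing changes. If not, add to Section 6.4.2.1:

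> LDD treatment should also be delayed if a Section 6.4.2.2 DLEQ or spontaneous-report criterion is met, until the additional testing has been done and the investigator has reviewed the result and documented the decision to proceed, postpone further, or contact the Sponsor about completing lock-in.

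Release rests on the investigator's review, so it need not wait for the independent expert reading named in the Synopsis. The three outcomes matter: a hold that ended only on a clear result would leave an unlocked lens with no way forward if evidence of damage were found.

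**Cost.** The DLEQ is already completed at each light visit, and the sponsor already accepts a delay for any tritan worsening. The downside is that some treatments may fall outside the 3-to-7-day window, leaving the lens unlocked for longer with UV spectacles worn. The length depends on how soon testing is done, and the documents do not bound it.

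As an illustration only, assume that each hold adds 7 days to the slowest schedule:

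| Holds | Final lock-in | Latest Months 1-2 visit (+14) | Days before Month 6 window opens (Day 120) |
|---|---|---|---|
| 0 | Day 52 | Day 66 | 54 |
| 1 | 52 + 7 = Day 59 | Day 73 | 47 |
| 4 | 52 + 28 = Day 80 | Day 94 | 26 |

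Under that assumption the study calendar has room. The table says nothing about the clinical effect of a longer unlocked period.

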6.4.2.3 Procedure Preparation

Protocol-required measurements should be completed prior to adjustment or lock-in treatments.

The subject should be prepared for light treatments as follows:

Once adequate pupil dilation is achieved, patch the subject's fellow eye and position the subject comfortably in front of the LDD with chin in the chinrest and forehead against the support bar. Ask the subject to grasp the handles on the LDD table for support. Inform the subject to concentrate on the green fixation light presented in front of them and to try and minimize eye movement.

6.4.2.4 Adjustment Procedure(s)

Refer to the LDD Operator's manual for instructions on LDD start up and instructions for the daily alignment test to be performed prior to the first treatment of the day to ensure the UV beam is aligned to the reticle. If the UV beam is not aligned to the reticle within the specifications detailed in the LDD Operator's manual, do not perform treatments and call RxSight customer service immediately.

- 1. All adjustment procedure(s) will be recorded.
- 2. Within the Patient ID and Patient Data screens, follow the touchscreen prompts to enter requested information. Press the "Proceed" button once information has been entered respectively for each screen.
- 3. Within the Confirmation screen, review all information and press the "Confirm" button.
- 4. Verify that the LDD ring lights and reticle target are activated.
- 5. Apply topical anesthetic.
- 6. Position the RxSight supplied contact lens (M = 0.766x) on the cornea using hydroxypropyl methylcellulose as the coupling medium.

Note: The RxSight contact lens is similar to those used in other ophthalmic procedures in which customized magnification is required. To ensure correct magnification for treatment, use only the RxSight designated contact lens.

- 7. Instruct the subject to focus straight ahead on the LDD fixation light with the study eye.
- 8. Using the microscope, focus on the cornea and verify that there are no trapped bubbles present. Confirm alignment of the contact lens by approximately aligning the Purkinje images to the inner circle of the reticle target.
- 9. Using the microscope, focus on the RxSight LAL haptics and align the reticle target with the periphery of the RxSight LAL.
- 10. Press the "Ready" button
- 11. Initiate the UV exposure as prompted by the LDD display using the trigger. Use the joystick to keep the RxSight LAL centered in the alignment reticle.
- 12. Perform micro adjustments to keep the reticle target centered to the RxSight LAL and to keep the RxSight LAL in focus. In the case of subject movement, loss of alignment, or loss of focus, pause the treatment, quickly refocus, realign the lens with respect to the reticle beam, and immediately resume treatment to limit the duration of any pauses once the light treatment has been initiated.

Note: Always maintain the RxSight LAL in focus by focusing at the haptics. Never focus onto the CCC (capsulotomy) or Purkinje images.

- 13. If the event of an aborted Adjustment Treatment, do not initiate a new treatment sequence; instead; instruct the subject to return 3-7 days later for refractive evaluation to assess whether an adjustment treatment is required or to proceed directly to a lock-in treatment.
- 14. Following the light adjustment, the subject will continue to wear their UV protective eyewear as instructed until exactly 24 hours after the final lock-in treatment has been completed.

The subject will return 3 to 7 days following the power adjustment treatment for another light treatment. The subject may receive up to 3 adjustment treatments before receiving the 1st lock-in treatment.

6.4.2.5 Lock-In Procedure(s)

Refer to the LDD Operator's manual for instructions on LDD start up and instructions for the daily alignment test to be performed prior to the first treatment of the day to ensure the UV beam is aligned to the reticle. If the UV beam is not aligned to the reticle within the specifications detailed in the LDD Operator's manual, do not perform treatments and call RxSight customer service immediately.

- 1. All lock-in procedure(s) will be recorded.
- 2. Within the Patient ID screen, utilize the pop-out menu within the Patient ID field to select the appropriate subject identification with eye to be treated. Reconfirm information displayed on screen and follow the touch screen prompts to enter in newly requested information. Press the "Proceed" button.
- 3. Within the Confirmation screen, review all information and press the "Confirm" button.
- 4. Verify that the LDD ring lights and reticle target are activated.
- 5. Apply topical anesthetic.
- 6. Position the RxSight supplied contact lens (M = 0.766x) on the cornea using hydroxypropyl methylcellulose or hypromellose as the coupling medium.

Note: The RxSight contact lens is similar to those used in other ophthalmic procedures in which customized magnification is required. To ensure correct magnification for treatment, use only the RxSight designated contact lens.

- 7. Instruct the subject to focus straight ahead on the LDD fixation light with the study eye.
- 8. Using the microscope, focus on the cornea and verify that there are no trapped bubbles present. Confirm alignment of the contact lens by approximately aligning the Purkinje images to the inner circle of the reticle target.
- 9. Using the microscope, focus on the RxSight LAL haptics and align the reticle target with the periphery of the RxSight LAL.
- 10. Press the "Ready" button

- 11. Initiate the irradiation delivery as prompted by the LDD display using the joystick or foot pedal to keep the RxSight LAL centered in the alignment reticle.
- 12. Perform micro adjustments to keep the reticle target centered to the RxSight LAL and to keep the RxSight LAL in focus. In the case of subject movement, loss of alignment, or loss of focus, pause the treatment, quickly refocus, realign the lens with respect to the reticle beam, and immediately resume treatment to limit the duration of any pauses once the light treatment has been initiated.

Note: Always maintain the RxSight LAL in focus by focusing at the haptics. Never focus onto the CCC (capsulotomy) or Purkinje images.

- 13. If the lock-in treatment is aborted before completion, contact the Sponsor for technical assistance.
- 14. Upon completion of the lock-in #1 treatment, a notification that indicates either "All required treatments complete" or "Lock-In #2 Required" will appear. If "All required treatments complete", proceed to step #16. If "Lock-In #2 Required", proceed to step #15.
- 15. The subject will return for the second lock-in treatment 3 to 7 days after the first lock-in treatment.
- 16. The subject will be permitted to discontinue wear of the UV protective eyewear exactly 24 hours after all lock-in treatments are completed.

